### **3. INTRODUCTION**

As per ICH E9 ([1](#)), the purpose of this document is to provide a more technical and detailed elaboration of the principal features of the analysis described in the protocol, and to include detailed procedures for executing the statistical analysis of the primary and secondary variables and other data.

This Trial statistical analysis plan (TSAP) assumes familiarity with the Clinical Trial Protocol (CTP). In particular, the TSAP is based on the planned analysis specification as written in CTP Section 7 “Statistical Methods and Determination of Sample Size”. Therefore, TSAP readers may consult the CTP for more background information on the study, e.g., on study objectives, study design and population, treatments, definition of measurements and variables, planning of sample size, randomisation.

Study data (including data entered in the RAVE EDC system and external data provided by suppliers) will be stored in a Clinical Data Repository (CDR).

Pharmacokinetic (PK) and pharmacodynamics (PD) parameters will be calculated using Phoenix WinNonlin™ software (version 6.3 or higher, Certara USA Inc., Princeton, NJ, USA).

The statistical analyses will be performed within the validated working environment CARE, including SAS™ (current Version 9.4, by SAS Institute Inc., Cary, NC, USA), and a number of SAS™-based tools (e.g., macros for the analyses of AE data or laboratory data; Report Appendix Generator system (RAGe) for compilation/formatting of the CTR appendices).

#### **4. CHANGES IN THE PLANNED ANALYSIS OF THE STUDY**

All analyses as planned in the CTP will be performed and are described in more detail in this TSAP.

## **5. ENDPOINTS**

### **5.1 PRIMARY ENDPOINTS**

#### **Section 2.1.2 of the CTP:**

*In Part 1 the following pharmacokinetic parameters will be determined for rosuvastatin:*

- *AUC0-∞ (area under the concentration-time curve of the analyte in plasma over the time interval from 0 extrapolated to infinity)*
- *Cmax (maximum measured concentration of the analyte in plasma)*

*In Part 2 the following pharmacokinetic parameters will be determined for dabigatran:*

- *AUC0-∞ (area under the concentration-time curve of the analyte in plasma over the time interval from 0 extrapolated to infinity)*
- *Cmax (maximum measured concentration of the analyte in plasma)*

### **5.2 SECONDARY ENDPOINTS**

#### **5.2.1 Key secondary endpoints**

This section is not applicable as no key secondary endpoints have been defined in the CTP.

#### **5.2.2 Secondary endpoints**

#### **Section 2.1.3 of the CTP:**

*In Part 1 the following pharmacokinetic parameter will be determined for rosuvastatin:*

- *AUC0-tz (area under the concentration-time curve of the analyte in plasma over the time interval from 0 to the last quantifiable data point)*

*In Part 2 the following pharmacokinetic parameter will be determined for dabigatran:*

- *AUC0-tz (area under the concentration-time curve of the analyte in plasma over the time interval from 0 to the last quantifiable data point)*

### **5.3.3 Safety endpoints**

**Section 2.2.2.4 of the CTP: Safety and tolerability of rosuvastatin, dabigatran and BI 1358894 will be assessed based on:**

- *Adverse events (including clinically relevant findings from the physical examination)*
- *Safety laboratory tests*
- *12-lead ECG*
- *Vital signs (blood pressure, pulse rate)*

## 6. GENERAL ANALYSIS DEFINITIONS

### 6.1 TREATMENTS

For basic study information on investigational products, assignment of treatment sequences and selection of doses, please see CTP, Sections 3 and 4.

The study consists of 2 trial parts. It is planned that 14 healthy male subjects each will enter either Part 1 or Part 2 of the study. Each part follows a non-randomised, open-label, two-period crossover design with a fixed sequence in healthy male subjects in order to compare the test (T1, T2) and reference (R1, R2) treatments as defined in Table 6.1: 1 below.

Table 6.1: 1 Treatments and labels used in the analysis

Treatment	Short label
Part 1	
R1 Rosuvastatin, 10 mg tablet, qd	Rosuvastatin
T1 BI 1358894, 2*100 mg tablet + Rosuvastatin, 10 mg tablet, qd	BI+Rosuvastatin
Part 2	
R2 Dabigatran etexilate, 150 mg capsule, qd	Dabigatran
T2 BI 1358894, 2*100 mg tablet + Dabigatran etex., 150 mg cap, qd	BI+Dabigatran

**Section 1.2.4 of the CTP:** *Based on an effective half-life of 33 h the Residual Effect Period (REP) of BI 1358894 has been determined to be 7 days. The REP for rosuvastatin and dabigatran is approximately 6 and 3 days, respectively. This is the period after the last dose with relevant measurable drug levels and/or pharmacodynamic effects is still likely to be present.*

The following separate study phases will be defined for the analyses of adverse events (AEs):

#### Part 1:

- **Screening** (ranging from 0:00 h on day of informed consent until first administration time of Rosuvastatin in treatment period 1)

- **On treatment**
  - **Rosuvastatin alone** (labelled “**Rosuvastatin**”, including REP; i.e. ranging from the time of first administration of Rosuvastatin in treatment period 1 until 6 days thereafter)
  - **BI+Rosuvastatin** (ranging from time of administration of BI 1358894 + Rosuvastatin in treatment period 2 until 7 days thereafter)
- **Follow-up (FU)** (labelled “**F/U Rosuvastatin**”, “**F/U BI+Rosuvastatin**”)
  - **F/U Rosuvastatin** (ranging from the end of REP of Rosuvastatin in treatment period 1 until the administration of BI+Rosuvastatin in period 2 or until trial termination, whatever occurs first)
  - **F/U BI+Rosuvastatin** (ranging from the end of REP of BI 1358894 in treatment period 2 until trial termination)

Part 2:

- **Screening** (ranging from 0:00 h on day of informed consent until first administration time of Dabigatran in treatment period 1)
- **On treatment**
  - **Dabigatran alone** (labelled “**Dabigatran**”) (ranging from the time of first administration of Dabigatran in treatment period 1 until 3 days thereafter)
  - **BI+Dabigatran** (ranging from time of administration of BI 1358894 + Dabigatran in treatment period 2 until 7 days thereafter)
- **Follow-up (FU)** (labelled “**F/U Dabigatran**”, “**F/U BI+Dabigatran**”)
  - **F/U Dabigatran** (ranging from the end of REP of Dabigatran in treatment period 1 until the administration of BI+Dabigatran in period 2 or until trial termination, whatever occurs first)
  - **F/U BI+Dabigatran** (ranging from the end of REP of BI 1358894 in treatment period 2 until trial termination)

**Section 7.3.4 of the CTP:** Note that AEs occurring after the last per protocol contact but entered before final database lock will be reported to Pharmacovigilance only and will not be captured in the trial database.

The following AE displays will be provided in the report:

Section 15.3 and Appendix 16.1.13.1.8 (for ClinicalTrials.gov and EudraCT only) of the CTR displays:

In these displays, the on-treatment phase will be analysed (labelled with the name of the study treatment (short label)). Screening and Follow up periods will not be included in this analysis.

The following totals will be provided in addition (Section 15.3 only):

- a total over all **on treatment phases** of study part 1 included in this analysis ("Total – Part 1")
- a total over all **on treatment phases** of study part 2 included in this analysis ("Total – Part 2")
- for ClinicalTrials.gov and EudraCT only: a total over all **on treatment phases** included in this analysis ("Total")

In Section 15.4 and Appendix 16.2 (Listings) of the CTR displays screening and follow-up periods will be included and no totals will be provided.

Table of vital signs will present results by the above mentioned on treatment phases (Rosuvastatin, BI+Rosuvastatin or Dabigatran, BI+Dabigatran).

For detailed information on the handling of the treatments refer to Technical TSAP ADS (analysis data set) plan and Analysis Data Reviewers guide.

In outputs for ClinicalTrials.gov and EudraCT both study parts will be combined in one table.

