#### **1.2.4 Residual Effect Period**

Based on an effective half-life of 33 h the Residual Effect Period (REP) of BI 1358894 has been determined to be 7 days. The REP for rosuvastatin and dabigatran is approximately 6 and 3 days, respectively. This is the period after the last dose with relevant measurable drug levels and/or pharmacodynamic effects is still likely to be present.

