### 7.8.1 Adverse Events

AEs will be coded with the most recent version of MedDRA.

The analyses of AEs will be descriptive in nature and will be based on BI standards as presented in “Analysis and Presentation of Adverse Event Data from Clinical Trials – Display Template” [BI-KMED-BDS-HTG-0041] (8). All analyses of AEs will be based on the number of subjects with AEs and not on the number of AEs.

For analysis multiple AE occurrence data on the eCRF will be collapsed into one AE provided that all of the following applies:

- All AE attributes are identical (lower level term (LLT), intensity, action taken, therapy required, seriousness, reason for seriousness, relationship, outcome, AE of special interest (AESI))
- The occurrences were time-overlapping or time-adjacent (time-adjacency of two occurrences is given if the second occurrence started within one hour after end of the first occurrence).

The analysis of AEs will be based on the concept of treatment emergent AEs. That means that all AEs will be assigned to screening or on-treatment phases as defined in [Section 6.1](#). AEs will be analysed based on actual treatments, as defined in [Table 6.1: 1](#)

**Section 5.2.6.1.4 of the CTP:** *The following are considered as AESIs:*

- **Hepatic injury**  
*A hepatic injury is defined by the following alterations of hepatic laboratory parameters:*
  - *An elevation of AST (aspartate transaminase) and/or ALT (alanine transaminase)  $\geq 3$ -fold ULN combined with an elevation of total bilirubin  $\geq 2$ -fold ULN measured in the same blood sample, or*
  - *Aminotransferase (ALT, and/or AST) elevations  $\geq 10$  fold ULN*

*These lab findings constitute a hepatic injury alert and the subjects showing these lab abnormalities need to be followed up according to the ‘DILI checklist’ provided in the ISF. In case of clinical symptoms of hepatic injury (icterus, unexplained encephalopathy, unexplained coagulopathy, right upper quadrant abdominal pain,*

*etc.) without lab results (ALT, AST, total bilirubin) available, the Investigator should make sure that these parameters are analysed, if necessary in an unscheduled blood test. Should the results meet the criteria of hepatic injury alert, the procedures described in the DILI checklist should be followed.*

According to ICH E3 (9), AEs classified as ‘other significant’ need to be reported and will include those non-serious and non-significant AE with

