- (i) ‘action taken = discontinuation’ or ‘action taken = reduced’, or
- (ii) marked haematological and other lab abnormalities or lead to significant concomitant therapy as identified by the Clinical Monitor/Investigator at a RPM.

An overall summary of AEs (including AESIs and other significant AEs) will be presented.

The frequency of subjects with AEs will be summarised by treatment, primary system organ class (SOC) and preferred term (PT). Separate tables will be provided for subjects with other significant AEs according to ICH E3 (9), for subjects with serious AEs, for subjects with drug-related AEs, for subjects with drug related serious adverse events and for subjects with AESIs. In addition, the frequency of subjects with AEs will be summarised by treatment, worst intensity, primary system organ class (SOC) and preferred term (PT).

The SOCs and PTs will be sorted by frequency (within SOC). The MedDRA version number will be displayed as a footnote in the respective output.

In addition, frequencies of subjects with non-serious AEs that had an incidence of > 5% for at least one treatment will be summarised by treatment, primary SOC and PT.

For disclosure of adverse events on EudraCT, additional information not included in a standard AE analysis will be performed. The following three entries will be created:

- Adverse Events per arm for disclosure on EudraCT
- Non-serious Adverse Events for disclosure on EudraCT
- Serious Adverse Events for disclosure on EudraCT

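### Part 2 AE tables count 3 days after dabigatran alone but 7 days after the combination; one equal-window table and a footnote would be a cheap improvement

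*SAP*

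**What the plan says.** Protocol 1.2.4 gives BI 1358894 a REP of 7 days, based on an effective half-life of 33 h, and adds: "The REP for rosuvastatin and dabigatran is approximately 6 and 3 days, respectively". Protocol 7.3.4 assigns AEs between intake and the end of the REP to treatment and later ones to follow-up. It says that treatments are compared descriptively, and it lets the SAP define further intervals.

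SAP 6.1 turns this into phases. For Part 2:

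- Dabigatran alone: "ranging from the time of first administration of Dabigatran in treatment period 1 until 3 days thereafter".
- BI 1358894 + dabigatran: "ranging from time of administration of BI 1358894 + Dabigatran in treatment period 2 until 7 days thereafter".
- Events later than 3 days after dabigatran alone go to a phase labelled F/U Dabigatran.

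For CTR Section 15.3 and the registry displays, "Screening and Follow up periods will not be included in this analysis". For Section 15.4 and the Appendix 16.2 listings, "displays screening and follow-up periods will be included and no totals will be provided". On the registry outputs: "In outputs for ClinicalTrials.gov and EudraCT both study parts will be combined in one table".

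SAP 7.8.1 states that AE analyses "will be based on the number of subjects with AEs and not on the number of AEs". It mentions no adjustment for length of observation. It also plans a table in which "frequencies of subjects with non-serious AEs that had an incidence of > 5% for at least one treatment will be summarised".

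**The concern.** A by-treatment AE table invites the reader to compare columns. In Part 2, an AE starting 5 days after the combination is counted in the test column. An AE starting 5 days after dabigatran alone is not counted in the reference column. The REP rule settles which treatment an event is attributed to. It does not make the two columns comparable.

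With 14 planned subjects, one event is visible. A non-serious AE in 1 of 14 subjects is 7.1%, which is enough to enter the table with the 5% threshold. In the registry output, columns with windows of 6, 7, 3 and 7 days stand side by side. At stake is a descriptive safety comparison that leans slightly against the combination. The PK endpoints are not involved.

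**Working it through.** **1. Do the windows match the protocol?** Yes: 3 and 7 days in SAP 6.1 are the REPs of protocol 1.2.4. The protocol gives no REP formula. For BI 1358894, five effective half-lives (the factor five is my assumption) are 5 × 33 h = 165 h = 6.9 days, which rounds to 7. For dabigatran, 3 days = 72 h, or 7.2 to 9 half-lives at the 10 to 8 h in protocol 1.2.3.

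**2. Does an equal window fit?** Protocol 3.1 separates the doses by at least 7 days. A 0 to 7 day window after dabigatran alone is the 3-day on-treatment phase plus the first 4 days of F/U Dabigatran.

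**3. How large is the window effect with no drug effect?** Let p(d) be the probability of at least one AE within d days of dosing, the same after both doses. Part 2 compares p(7) with p(3). If s is the share of subjects with an AE by day 7 whose first AE starts after day 3, then

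ratio = p(7)/p(3) = 1/(1 − s).

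Thus s = 5% gives 1.05, 10% gives 1.11 and 30% gives 1.43. The documents do not give s.

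**4. Range under stated assumptions.** Take p(d) = 1 − exp(−H(d)), with H(d) proportional to 1 − 2^(−d/h) for a hazard that halves every h days, or to d for a constant hazard. Scale H so that p(7) = 20% (assumed; range 7% to 50%). Then H(7) = −ln 0.8 = 0.2231.

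Worked case, h = 1 day: H(3) = 0.2231 × (1 − 2^−3)/(1 − 2^−7) = 0.2231 × 0.8819 = 0.1968. So p(3) = 17.9% and the ratio is 20/17.9 = 1.12.

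| Hazard half-life | p(3) | Expected subjects of 14, reference vs test | Excess | Ratio (range for p(7) = 7% to 50%) |
|---|---|---|---|---|
| 0.5 day | 19.7% | 2.76 vs 2.80 | 0.04 | 1.01 (1.01–1.02) |
| 1 day | 17.9% | 2.50 vs 2.80 | 0.30 | 1.12 (1.09–1.13) |
| 2 days | 14.6% | 2.05 vs 2.80 | 0.75 | 1.37 (1.29–1.40) |
| 4 days | 12.1% | 1.69 vs 2.80 | 1.11 | 1.66 (1.52–1.71) |
| Constant | 9.1% | 1.28 vs 2.80 | 1.52 | 2.19 (1.95–2.29) |

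If the hazard does not rise after dosing, the constant-hazard row is the upper bound.

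**5. Chance of an apparent difference.** Treat the two counts as independent Binomial(14) variables. This is a simplification, because the same men contribute to both. At p(7) = 20%, the chance that test exceeds reference, against the reverse, is 41% vs 40% (0.5 day), 46% vs 35% (1 day), 55% vs 26% (2 days) and 71% vs 13% (constant).

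**6. Part 1 for contrast.** With 6 and 7 days, the ratio is 1.00 to 1.04 for half-lives up to 2 days and 1.15 for a constant hazard at 20%.

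**7. Which rows are plausible?** In the Part 2 Flow Chart as read (the table may be broken), no AE questioning is scheduled between 48 h and the next admission or the end-of-trial visit, in either period. AEs are still recorded throughout, but recording of late onsets is likely to be thinner. This makes the constant-hazard row less likely.

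**The case against.** The strongest reply is that nothing in the plan is wrong. The windows are prespecified and REP-based, and SAP 6.1 applies protocol 7.3.4 as written. Only period 2 contains BI 1358894, so only there do days 3 to 7 fall within a REP. The protocol permits further intervals but does not require them. All of this stands.

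Other displays soften the effect. SAP 7.8.1 plans separate tables of drug-related AEs and drug-related serious AEs. Protocol 5.2.6.1.6 counts implausible onset time as an argument against causality, so unrelated late events can be separated there. Protocol 7.3.4 summarises follow-up by previous treatment, and F/U Dabigatran appears in Section 15.4 and the listings. With 14 subjects, a reader who has these can rebuild days 3 to 7. This mitigates the problem but leaves the reconstruction to the reader.

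The direction is cautious: the rule removes no event from the test column, no hypothesis is tested on these tables, and the trial stopping criteria in protocol 3.3.4.3 do not refer to these windows. Equal days would also not mean equal ascertainment. After dabigatran alone, days 3 to 7 are next asked about at the period 2 admission; after the combination, at the end-of-trial visit on day 8 to 21. This too stands.

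A reader might infer three stronger things that the documents do not support:

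- **That the SAP contradicts the protocol.** It does not.
- **That test AE rates will be inflated by 7/3 = 2.33.** That is the ratio of window lengths. It would be approached only with rare events and a constant hazard.
- **That no equal-window display exists anywhere.** SAP 6.1 refers to a technical analysis data set plan, and SAP 7.8.1 to a display template. Neither is available here, so the statement is limited to the visible text.

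**Conclusion.** This is a minor point about presentation, not an error. The by-treatment AE columns in Part 2 rest on windows of 3 and 7 days, and the visible text sets no equal-window display beside them. The direction follows from the windows, given no drug effect and the same hazard after each dose. The size does not: it rests wholly on assumed incidence and onset timing. At an assumed 20% by day 7, the excess is 0.04 to 0.75 of one subject in 14 for half-lives of 0.5 to 2 days, and at most 1.52 subjects if the hazard does not rise. If AEs cluster in the first day or two, the effect is small.

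Only the window lengths, the minimum dose interval and the planned 14 subjects come from the documents. The fixed sequence confounds treatment with period whatever window is used.

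**What to change.** Keep the REP-based tables as the standard display.

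1. In SAP 6.1 and 7.8.1, define one further Part 2 interval, as protocol 7.3.4 allows: 0 to 7 days after dosing for both treatments, ending at the period 2 dose if that is earlier. Add one supplementary AE frequency table on it, by treatment, system organ class and preferred term.
2. In the Section 15.3 and registry tables, footnote each column's window unless the template already does so: Rosuvastatin 6 days, BI+Rosuvastatin 7, Dabigatran 3, BI+Dabigatran 7. For Part 1 the footnote is enough.

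The cost is SAP wording, a footnote and one table. No new data are needed, because AEs are recorded throughout. The drawback is that some events after the dabigatran REP count for reference in the supplementary table. The table removes neither the period confounding nor the different timing of AE questioning for days 3 to 7.

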## **6.2            IMPORTANT PROTOCOL DEVIATIONS**

Data discrepancies and deviations from the CTP will be identified for all treated subjects.

**Section 7.3 of the CTP:** *Important protocol deviation (IPD) categories will be suggested in the IQRM plan, IPDs will be identified no later than in the Report Planning Meeting, and the IPD categories will be updated as needed.*

Consistency check listings (for identification of deviations of time windows) and a list of protocol deviations (e.g. deviations in drug administration, in blood sampling times, etc.) will be provided to be discussed at the report planning meeting (RPM). At this meeting, all manual deviations identified at the sites by the CRAs and deviations too complex to program will be reviewed by the trial team to decide which are considered important. For definition of important protocol deviations (iPD), and for the process of identification of these, refer to the Boehringer Ingelheim (BI) SOP "Identify and Manage Important Protocol Deviations (iPD)" (2).

If any iPDs are identified, they are to be summarised into categories and will be captured in an accompanying Excel spreadsheet (3). Categories which are considered to be iPDs in this trial are defined in the integrated quality and risk management plan (IQRMP). If the data show other iPDs, the definition in the IQRMP will be supplemented accordingly by the time of the Report Planning Meeting.

The iPDs will be summarised and listed.

### 6.3 SUBJECT SETS ANALYSED

#### Section 7.3 of the CTP:

- *Treated set (TS): The treated set includes all subjects who were entered and treated with at least one dose of study drug. The treated set will be used for safety analyses.*
- *Pharmacokinetic parameter analysis set (PKS): This set includes all subjects in the treated set (TS) who provide at least one PK endpoint that was defined as primary or secondary and was not excluded due to a protocol deviation relevant to the evaluation of PK or due to PK non-evaluability (as specified in the following subsection 'Pharmacokinetics'). Thus, a subject will be included in the PKS, even if he contributes only one PK parameter value for one period to the statistical assessment. Descriptive and model based analyses of PK parameters will be based on the PKS.*  
PKS also will be used for the descriptive analyses of PD parameters.

[...]

*Plasma concentration data and parameters of a subject will be included in the statistical pharmacokinetic (PK) analyses if they are not flagged for exclusion due to a protocol deviation relevant to the evaluation of PK (to be decided no later than in the Report Planning Meeting) or due to PK non-evaluability (as revealed during data analysis, based on the criteria specified below). Exclusion of a subject's data will be documented in the CTR.*

*Relevant protocol deviations may be*

- *Incorrect trial medication taken, i.e. the subject received at least one dose of trial medication the subject was not assigned to*
- *Incorrect dose of trial medication taken*

*Plasma concentrations and/or parameters of a subject will be considered as non-evaluable, if for example*

- *The subject experienced emesis that occurred at or before two times median  $t_{max}$  of the respective treatment (Median  $t_{max}$  is to be determined excluding the subjects experiencing emesis),*
- *A pre-dose concentration is  $>5\% C_{max}$  value of that subject*
- *Missing samples/concentration data at important phases of PK disposition curve*

The descriptive analysis of PK concentrations will be based on the ADS ADPC as described at the beginning of [Section 7](#).

Table 6.3: 1 Subject sets analysed

Class of endpoint	Subject set	
	TS	PKS
Analyses of PK/PD endpoints		X
Safety parameters	X	
Demographic/baseline parameters	X	
Important protocol deviations	X	
Disposition	X	

